#### ***7.1.1.6 Adverse events of special interest (AESIs)***

AESIs include anaemia (or haemodilution), hepatic disorders, oedema / fluid retention and decompensation/aggravation of heart failure. These are defined using MedDRA version 24.0 in Appendix 14.3.

### 7.1.2 Analysis

An overview table will be provided displaying by study part (DB, SB aprocitentan or DB-WD) and treatment group (within each study part) the number (%) of subjects with at least one treatment-emergent: AE, SAE, AE leading to premature discontinuation of study treatment, AESI, MACE and MACE-plus (the latter two as confirmed by adjudication).

A similar overview table (but without study part and treatment group) will also be provided for run-in-emergent AEs based on the RIS.

Treatment-emergent AEs will be tabulated by study part (DB, SB aprocitentan or DB-WD), and treatment group (within each study part), SOC and PTs within each SOC: the number and percentage of subjects who experienced at least one AE, at least one AE within each SOC and at least one AE within each PT will be displayed. AEs will also be summarized by decreasing frequency of PT in the aprocitentan 25 mg group.

A similar table (but without study part and treatment group) will also be provided for run-in-emergent AEs based on the RIS.

AEs will also be tabulated by maximum intensity and relationship to aprocitentan or placebo. Relationship to standardized background antihypertensive therapy will only be listed.

If an AE starts in one study part and ends in the next part without increasing intensity, it is counted only in the first part.

Treatment-emergent SAEs will be summarized in a similar manner as AEs.

For EudraCT purposes, non-serious and total death / serious AEs will be summarized separately by study part.

AEs leading to premature discontinuation of study treatment will be summarized in a similar manner as AEs. AESI (except hepatic disorders) will be summarized by CKD stage at Baseline.

The time from Randomization to (first) oedema / fluid retention AESI in the DB or SB aprocitentan part will be summarized by treatment group using Kaplan-Meier plots (supplemented by a table displaying the numbers of subjects at risk, those with an event, and those censored by treatment group, using weekly intervals). For subjects without oedema / fluid retention, the time will be censored at the last dose of DB or SB treatment, whichever comes last. Additionally, a 'two-step' Cox model with a factor for treatment will be fitted [see Section 8.2 for details].

The time from Re-randomization to (first) oedema / fluid retention in the DB-WD part will be summarized similarly. For subjects without oedema / fluid retention, the time will be censored at the last DB-WD treatment + 30 days (or EOS date, whichever comes first)

The time from Randomization or Re-randomization to (first) oedema / fluid retention AESI in the DB or DB-WD will be summarized by CKD stage at Baseline.

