### 7.1 Adverse events

#### 7.1.1 Variables

##### 7.1.1.1 Treatment-emergent adverse events

The original terms used by the investigators to describe AEs in the **Adverse Events** eCRF are assigned a PT and a SOC for classification and tabulation using MedDRA (last available version).

Subjects who experienced the same AE more than once within a specified time period (as qualified by the same PT) are counted only once.

An event/assessment is treatment-emergent if the onset/assessment date is between the start date of the randomized treatment period up to EOT+30 days (begin and end dates included). More in particular:

- An event/assessment is DB treatment emergent if the onset/assessment date is between the start date of the DB part up to the day before the start date of the SB treatment part (or EOT + 30 days if the subject did not enter the SB part);

- An event/assessment is SB treatment emergent if the onset/assessment date is between the start date of the SB aprocitentan part up to the day before the start date of the DB-WD treatment part (or EOT + 30 days if the subject did not enter the DB-WD part);
- An event/assessment is DB-WD treatment emergent if the onset/assessment date is between the start date of the DB-WD part up to EOT + 30 days.

An event/assessment with an onset/assessment date between the start date of the run-in period up to the start of randomized treatment period (if the subject is randomized; EOT if the subject is not randomized) will be designated as run-in-emergent.

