## 7.6 Other safety variables and analyses

### 7.6.1 Treatment-emergent MACE and MACE-plus

MACE is defined as cardiovascular death, non-fatal myocardial infarction, or non-fatal stroke. MACE-plus includes, in addition, hospitalization for heart failure. The analyses will focus on MACE-plus.

Treatment-emergent MACE-plus events confirmed by the CAC are reported on the **Consensus Event Adjudication Form**. The number (%) of subjects with confirmed MACE-plus and sub-categories (i.e., death, non-fatal myocardial infarction, non-fatal stroke, or hospitalization for heart failure) will be tabulated by study part (DB, SB aprocitentan, or DB-WD) and treatment group (within study part). MACE-plus will be summarized by CKD stage at Baseline.

If there are *at least 12* subjects with an adjudication confirmed MACE-plus, the time from Randomization to (first) MACE-plus in the DB or SB aprocitentan part will be summarized by treatment group using Kaplan-Meier plots (supplemented by a table displaying the numbers of subjects at risk, with an event and censored by treatment group, using weekly intervals). For subjects without MACE-plus, the time will be censored at the last dose of DB or SB treatment (whichever comes last). Additionally, a ‘two-step’ Cox model with a factor for treatment will be fitted [see Section 8.2 for details].

If there are *at least 12* subjects with an adjudication confirmed MACE -plus, the time from Re-randomization to (first) MACE-plus in the DB-WD part will be summarized similarly, except that the Cox model is the conventional one. For subjects without MACE-plus, the time will be censored at the last dose of DB-WD treatment + 30 days (or EOS date, whichever comes first).

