### 10.1 Analysis periods and visit windows

#### 10.1.1 Analysis periods

The **screening period** is defined as the time from the informed consent date until one day before the run-in period start date (or EOS if the subject does not enter the run-in).

The **RI period** begins at the date of the first dose of RI treatment and ends at the date of the last dose of RI treatment, collected on the **Study Treatment Log** where ‘Study Period’ is ‘Single Blind Run-in’.

The **randomized treatment period** begins at the DB treatment start date and ends at the *last* of the treatment stop dates collected on the **Study Treatment Log** where ‘Study Period’ is not ‘Single Blind Run-in’ and the reason for treatment end is not ‘Interruption due to an AE’ or ‘Interruption not due to an AE’.

The randomized treatment period is divided into three parts: DB, SB aprocitentan and DB-WD.

- The DB part begins at the DB treatment start date and ends at the DB treatment stop date collected on the **Study Treatment Log** where ‘Study Period’ is ‘Double-Blind Treatment (Part 1)’ and the reason for treatment end is not ‘Interruption due to an AE’ or ‘Interruption not due to an AE’.
- The SB aprocitentan part begins at the SB treatment start date and ends at the SB treatment stop date collected on the **Study Treatment Log** where ‘Study Period’ is ‘Single-Blind Treatment (Part 2)’ and the reason for treatment end is not ‘Interruption due to an AE’ or ‘Interruption not due to an AE’.
- The DB-WD part begins at the DB-WD treatment start date and ends at the DB-WD treatment stop date collected on the **Study Treatment Log** where ‘Study Period’ is ‘Double-Blind Withdrawal Treatment (Part 3)’ and the reason for treatment end is not ‘Interruption due to an AE’ or ‘Interruption not due to an AE’.

Should there be any ‘gap’ between the end of one period and the start of the next, then the gap days are allocated to the former period. In the unlikely case that the gap is more than 30 days, gap days 31, 32, etc. will not be allocated to a study part.

The **safety FU period** begins one day after the end of the randomized treatment period and ends at the date of the EOS visit. Safety data obtained during the safety FU period or at the EOS visit will be allocated to the last part of the subject’s randomized treatment period. This is restricted to data collected up to EOT+30 days. Safety data collected beyond that time point will not be allocated to a study part.

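### The DB+SB time-to-event safety analyses count events up to 30 days after the last dose but censor event-free subjects at the last dose, which modestly overstates Kaplan-Meier incidence

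*SAP*

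**What the plan says.** **Which events count.** SAP 7.1.2 analyses the first oedema / fluid retention event in the DB or SB part. SAP 7.1.1.1 says when an event belongs to a part. For DB, the window closes the day before SB starts, "or EOT + 30 days if the subject did not enter the SB part". For SB, it closes the day before DB-WD starts, "or EOT + 30 days if the subject did not enter the DB-WD part". SAP 10.1.1 agrees: "Safety data obtained during the safety FU period or at the EOS visit will be allocated to the last part" of the subject's randomised treatment, up to EOT + 30 days.

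**When event-free subjects are censored, DB+SB.** For oedema / fluid retention, "the time will be censored at the last dose of DB or SB treatment, whichever comes last" (SAP 7.1.2). For MACE-plus, "the time will be censored at the last dose of DB or SB treatment (whichever comes last" (SAP 7.6.1). SAP 7.6.2 handles diuretic increase or addition in the same way as MACE-plus. The MACE-plus survival analysis, and by reference the diuretic one, is conditional on at least 12 affected subjects; the oedema analysis is unconditional.

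**When event-free subjects are censored, DB-WD.** For oedema / fluid retention, "the time will be censored at the last DB-WD treatment + 30 days (or EOS date, whichever comes first" (SAP 7.1.2). SAP 7.6.1 uses the same rule for MACE-plus in DB-WD.

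**Data available.** The footnotes to SAP Table 2 require adverse events to be reported for 30 days after study treatment is discontinued, whether or not the subject has had an event.

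**The concern.** Kaplan-Meier and Cox methods require that being at risk at time *t* does not depend on what happens after *t*. Here it does. Take two subjects who take their last SB dose on the same day. The one who develops oedema 20 days later stays in the risk set for those 20 days and then counts as an event. The one who stays well is removed on the day of the last dose, although observed for the same 30 days. The post-treatment events are kept and most of the post-treatment time at risk is discarded.

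This matters because oedema / fluid retention is the only adverse event of special interest with a time-to-event analysis, and the subjects affected are those who stop early. The DB-WD analyses pair a 30-day event window with 30-day censoring, so the SAP already contains the matched rule and does not apply it to DB+SB.

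**Working it through.** The documents state no incidence, event count or hazard ratio for these analyses, so there is no planned figure to reproduce. The check has three steps.

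**1. A small example.** The Kaplan-Meier estimate is S(t) = Π(1 − d/n) over event times, with d events among n at risk. Suppose ten subjects stop at Day 100, one of them has an event at Day 120, and ten others continue event-free to Day 252.
- SAP rule: at Day 120 the risk set is the one future case plus the ten continuing subjects, n = 11. Incidence = 1/11 = 9.1%.
- Matched rule (event-free stoppers kept to Day 130): n = 20. Incidence = 1/20 = 5.0%.

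The events are the same and the SAP-rule risk sets are never larger, so the SAP-rule incidence cannot be the lower of the two.

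**2. Approximate size.** If subjects stop at daily rate γ, each stop discards up to 30 days at risk, so the event rate is inflated by about 1 + 30γ. Inputs:
- Time to Week 36: 252 days (SAP Table 2).
- Planned loss between randomisation and re-randomisation: 1 − 380/600 = 36.7% (SAP 2.1). Observed loss was lower than expected, with no figure given, so 10% and 20% are also used as assumptions.

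With γ = −ln(1 − loss)/252:
- 10% loss: γ = 0.1054/252 = 0.00042, factor 1.013
- 20% loss: γ = 0.2231/252 = 0.00089, factor 1.027
- 36.7% loss: γ = 0.4568/252 = 0.00181, factor 1.054

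**3. Simulation.** Two million subjects per scenario, exponential stopping and event times, EOT taken as the last dose, full 30-day follow-up for every stopper, and no extension for subjects who continue. True Week 36 incidence (5% or 20%) and equal hazard on and off drug are assumptions.

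| Loss | True 5%: SAP rule / matched | Ratio | True 20%: SAP rule / matched | Ratio |
|---|---|---|---|---|
| 10% | 5.07 / 5.01 | 1.012 | 20.20 / 19.99 | 1.011 |
| 20% | 5.12 / 5.00 | 1.024 | 20.44 / 20.00 | 1.022 |
| 36.7% | 5.29 / 5.03 | 1.052 | 20.95 / 20.03 | 1.046 |

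Against the matched 30-day rule, the event-rate inflation hardly changes with the hazard after stopping. Against a purely on-treatment analysis it does. At 36.7% loss the event-rate ratio is about 1.03, 1.05 and 1.15 to 1.16 for a post-dose hazard 0.5, 1 and 3 times the on-treatment hazard.

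**Between arms.** With equal true hazards but unequal stopping (assumed figures), the simulated event-rate ratio should be 1.00. Under the SAP rule it was:
- DB, 5% versus 2% stopping: 1.02
- DB, 10% versus 2% stopping: 1.04
- DB+SB, 36.7% versus 20% stopping: 1.02

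The matched rule gave 1.00 to within simulation error in each case. If the arms are exchanged the ratio inverts: 1/1.04 = 0.96.

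**The case against.** The strongest reply is that the event window is inferred. SAP 7.1.2 does not repeat the 30-day window for the survival analysis, and SAP 2.3 and 10.1.1 define each part as ending when its treatment ends. On that reading only on-treatment events count and last-dose censoring matches them. This does not hold up well. SAP 10.1.1 goes on to allocate follow-up safety data to the last treated part, 7.1.1.1 gives the 30-day window explicitly, and the section on MACE-plus is headed as treatment-emergent. Nothing restricts the DB+SB analyses to events up to the last dose. If that was intended, the text has to say so.

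Several other points stand and limit the concern:
- Only subjects who stop without entering the next part are affected. For those who continue, only gap days remain.
- The upper end of the range uses the planned loss, and observed drop-out was below it. Stoppers who die, withdraw or are lost contribute less than 30 days, which reduces the effect further.
- The placebo-controlled period is short. If the 5% expected to lack a Week 4 reading (SAP 6.2.2) all stopped evenly over 28 days, the lost time at risk is about 0.05 × 14/28 = 2.5%. After that everyone receives 25 mg, and SAP 8.2.4 itself acknowledges that comparing SB by earlier treatment is rather artificial.
- These are safety displays outside the confirmatory testing strategy, and the planned weekly numbers at risk would show a thin tail.

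**Conclusion.** The concern holds as a mismatch between event and censoring windows in the DB+SB Kaplan-Meier and two-step Cox analyses of oedema / fluid retention and, where at least 12 subjects have an event, of MACE-plus and diuretic increase or addition. Relative to a matched 30-day rule, the direction for Kaplan-Meier incidence is certain and the size modest: about 1% to 5% relative at Week 36 for 10% to 37% loss. This rests on assumed event rates, constant stopping and equal hazard on and off drug. Counts of subjects with events by study part are unaffected.

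A reader might infer three stronger conclusions, which the documents do not support:
- *Hazard ratios are biased upwards.* The direction depends on which arm stops more, and the documents give no stopping rates by arm. With equal stopping the inflation largely cancels.
- *The curves will jump to extreme values at the end.* That depends on how many SB completers are not re-randomised, which the documents do not state, and on the timing of Visit 11, which the COVID-19 addendum allows to run up to 8 weeks late.
- *The DB+SB curves cannot be compared with the DB-WD curves.* The SAP plans no such comparison, and the two differ in population and time origin anyway.

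**What to change.** In SAP 7.1.2 and 7.6.1 (and so 7.6.2), censor event-free subjects in the DB+SB analyses at the earliest of:
- last DB or SB dose + 30 days, whichever part was last;
- EOS date;
- the day before the first DB-WD dose.

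This mirrors the existing DB-WD rule. Use one anchor for events and censoring: the EOT visit may fall up to 7 days after the last dose (footnote to SAP Table 2), so state whether EOT + 30 days runs from the visit or the dose.

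If an on-treatment analysis is intended instead, keep last-dose censoring and state that only events up to the last dose count. The version not chosen can serve as a sensitivity analysis.

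The cost is one sentence in each of two sections and one derivation. No new data are needed, because adverse events are already collected for 30 days after treatment stops.

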## 7.2 Death

Death information is taken from the **Death** eCRF. The primary cause of death is reported on the same form.

The number (%) of deaths will be tabulated by study part (DB, SB aprocitentan and DB-WD) and treatment group (within study part).

All deaths will be listed, along with the original terms used by the investigator to describe the primary death cause and associated MedDRA PTs.

## 7.3 Laboratory tests

### 7.3.1 Variables

Laboratory assessments are performed according to the schedule of assessments [Table 1 and Table 2]. Laboratory data are evaluated in SI units as provided by the central laboratory. The following tests are considered:

- Hematology: hemoglobin, hematocrit, erythrocyte count, reticulocyte count, leukocyte count with differential counts, platelet count, mean corpuscular volume.
- Clinical Chemistry: aminotransferases (aspartate aminotransferase [AST] / alanine aminotransferase [ALT]), alkaline phosphatase, bilirubin and direct bilirubin, cholesterol, triglyceride, high density lipoprotein, low density lipoprotein, creatinine, eGFR (estimated using the CKD-EPI creatinine equation), urate, albumin, protein, glucose, sodium, potassium.
- Urinalysis: UACR.

For women of childbearing potential, urine as well as serum pregnancy tests are performed, but these results will not be summarized as part of the laboratory data. Positive pregnancy tests (if any) will be reported.

Results of local laboratory tests (collected on the **Local Laboratory Hematology** and **Local Laboratory Clinical Chemistry** eCRF) will not be used in summaries but will be listed.

Laboratory marked abnormalities are defined in Section 14.2. When determining double-blind treatment-emergent marked laboratory abnormalities, all assessments (including the unscheduled ones) are considered.

All assessments (including the unscheduled ones) are considered and re-assigned to the most appropriate visit according to the rules described in Section 10.1.2.

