      - Due to the current circumstances, even more flexibility is allowed (e.g., skipping visits) based on the investigator's judgment by taking into consideration a subject's medical condition (e.g., BP level, ongoing adverse events).
  - **Double-blind withdrawal part 3, protocol section 3.1.1.3:** The key visits are Visit 13 (Re-randomization) and Visit 15 (Week 40) as BP measurements collected during these two visits are needed to derive the study key secondary endpoint. The visit window for these two visits can be  $\pm 1$  week. If this is not possible, the Idorsia study team must be contacted as soon as possible to evaluate potential alternatives.

- **Laboratory assessments, protocol section 7.2.3.5:** If blood and urine samples cannot be collected by the courier for shipment to the central laboratory, site staff should make sure that, in addition to freezing the samples for delayed assessments, a portion of the sample is used to measure the following safety parameters by the site's local laboratory:
  - Hemoglobin, NT-proBNP, serum creatinine, eGFR, ALT, AST, and total bilirubin.

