#### **2) During the call**

- Ask the subject for the measured BP and body weight values and record them in the subject's medical chart.
  - Remind the subject to bring the home BP monitoring card or the notebook to the next on-site visit for verification.
- Ask for adverse events, follow the same process as for site visit, i.e., use an open-ended question such as: "Have you had any medical problem since the last study visit?"

- Ask whether any new medication has been taken or other medication has been modified.
- **Study treatment, protocol section 5:**
  - Remind the subject about the importance of taking study medications according to the protocol.
  - Check if the subject has enough study treatment and SBAT to ensure no study treatment and/or SBAT holiday. If the subject does not have enough study treatment and/or SBAT to last until the next visit, follow the instructions below:
    - If possible, the subject or a relative can collect study treatment and/or SBAT from the site (e.g., at a specific site delivery point / at the gate of the clinic).
    - If the above option is not possible, study treatment and/or SBAT may be sent to the subject's home using a local courier organized by site or through the site's CRA.
    - If neither of the above options are possible, the site's CRA is to be contacted. Idorsia will support the site and the CRA to find the best solution for the subject (e.g., collect SBAT from the local pharmacy).
- **Laboratory assessments, protocol section 7.2.3.5:**
  - For subjects with a medical history of heart disease and/or fluid retention/edema, ongoing adverse events related to cardiovascular diseases, or eGFR between 15 and 30 mL/min/1.73 m^2, the following blood parameters must be measured: hemoglobin, NT-proBNP, serum creatinine, eGFR, ALT, AST, and total bilirubin.
    - If a subject is allowed to leave the house according to the local regulations, assist him/her to find a local laboratory close to his/her home for the above measurements. Provide a prescription for the tests to be performed. Costs incurred will be reimbursed by Idorsia.
    - If a subject is not allowed to leave the house according to the current local regulations, organize the drawing of blood samples at the subject's home. In the event of difficulties, the site's CRA can be contacted for support.

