## 2.4 Impact of the COVID-19 pandemic

Idorsia provided instructions and guidance in line with Health Authority guidelines (FDA, EMA and individual national health authorities) released in March 2020. These recommendations and instructions are summarized in an addendum of the protocol [D-20.063]. The impact on the statistical analysis is addressed in Sections 2.4, 5.1.2, 5.1.3, 5.2, 6.2.7, 6.3.7, 6.5.1 and 6.5.2 of this SAP.

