### 7.3.2 Analysis

Changes from baseline for laboratory tests to visits in the DB+SB part will be summarized using descriptive statistics by visit and treatment group (in the DB part). Changes from DB-WD baseline (Week 36) to visits in the DB-WD part and up to EOS will be summarized by visit and treatment group (in the DB-WD part). Data will be displayed in SI units whenever possible and graphical approaches will be applied for certain variables.

Percentage changes from baseline in plasma volume to visits in the DB+SB part will be estimated based on baseline (V4) as well as post-baseline (Vx) in hemoglobin and hematocrit (as a fraction between 0 and 1) using the following formula [[Strauss 1951](#)]:

$$\text{estimated change} = 100 \times \frac{\text{hemoglobin (V4)}}{\text{hemoglobin(Vx)}} \times \frac{1 - \text{hematocrit (Vx)}}{1 - \text{hematocrit(V4)}} - 100$$

Percentage changes from Week 36 (V11) in plasma volume to visits in the DB-WD part will be estimated similarly but with V4 replaced by V11. Estimated changes in plasma volume will be summarized by visit and treatment group (in the DB+SB part or DB-WD part, where appropriate).

The number (%) of subjects with laboratory marked abnormalities will be tabulated by study part (DB, SB, and DB-WD) and treatment group (within study part). In addition, the number (%) of subjects with AST or ALT > 3 × the ULN combined with bilirubin > 2 × ULN will be tabulated. In addition, AST or ALT > 5 or 10 × ULN will also be tabulated.

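### Safety bloods that the COVID-19 addendum sends to local laboratories are listed but not summarised, so an abnormality seen only on a local result is missing from the marked-abnormality and liver tables

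*SAP*

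**What the plan says.** **SAP 7.3.1.** The source of the analysed values is stated first: "Laboratory data are evaluated in SI units as provided by the central laboratory". Results on the two local-laboratory eCRFs "will not be used in summaries but will be listed". The same section says that, for double-blind treatment-emergent marked abnormalities, "all assessments (including the unscheduled ones) are considered".

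**SAP 7.3.2.** "The number (%) of subjects with laboratory marked abnormalities will be tabulated by study part", and by treatment group within each part. A further count covers AST or ALT above 3 × ULN combined with bilirubin above 2 × ULN, and higher AST/ALT cut-offs are also tabulated.

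**Addendum 2.1.2, During the call.** The group is defined by history and current events: "For subjects with a medical history of heart disease and/or fluid retention/edema, ongoing adverse events related to cardiovascular diseases". Subjects whose eGFR lies in the range 15 to 30 mL/min/1.73 m² also belong to it. In this group "the following blood parameters must be measured: hemoglobin, NT-proBNP, serum creatinine, eGFR, ALT, AST, and total bilirubin". A subject who may leave home is helped to find a nearby local laboratory; otherwise blood is drawn at home. The local laboratory report is the source document, and the contact is entered as an unscheduled visit.

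**Addendum 2.1.2, Study visits.** A call does not stand in for the on-site visit, which must follow as soon as possible. It is skipped only if it could not be held until within 1 week of the next scheduled visit.

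**SAP 2.4.** The pandemic's effect on the analysis is "addressed in Sections 2.4, 5.1.2, 5.1.3, 5.2, 6.2.7, 6.3.7, 6.5.1 and 6.5.2 of this SAP". No part of Section 7 is in that list.

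**The concern.** Excluding local results does no harm when they duplicate central ones. The only local sample in the SAP's ordinary schedule is of that kind: the Visit 4 eligibility sample, drawn alongside a central one (Table 1, footnote 17). Under the addendum a local result can instead be the only result for a contact, and the exclusion was not revisited.

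At stake is the count of subjects with marked abnormalities and with combined AST/ALT and bilirubin elevations. Leaving out local-only results can lower these counts but cannot raise them. The measurements left out are ones the addendum made compulsory because of the subject's history or condition.

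The wording also leaves room for two readings. Remote contacts are unscheduled visits, and unscheduled assessments are to be considered, yet local results are barred from summaries. The specific sentence on local results most plausibly governs, but two programmers could build different tables.

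**Working it through.** The plan states no figure on this point, so there is none to reproduce. The check compares the rules and counts the scheduled samples.

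**1. Which parameters are affected.** The addendum names seven.

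| Parameter | Threshold in SAP 14.2 | Needs a laboratory ULN? |
|---|---|---|
| Haemoglobin, low | < 100 and < 80 g/L | No |
| Haemoglobin, high | rise above ULN, or above baseline if that exceeds ULN | Yes |
| eGFR | < 60 and < 30 mL/min/1.73 m² | No |
| Creatinine | multiple of ULN, or of baseline if that exceeds ULN | Yes |
| ALT, AST | multiples of ULN | Yes |
| Total bilirubin | multiples of ULN | Yes |
| NT-proBNP | none (summarised under SAP 7.6.3) | Not applicable |

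Six of the seven could therefore produce a marked abnormality.

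**2. Does a local-only value reach the tables?** Both 7.3.2 tables are summaries, 7.3.1 bars local values from summaries, and SAP 2.4 points to no exception. A local-only value does not reach them. For home draws this assumes analysis in a local laboratory. The addendum does not name the laboratory, but its next instruction treats a local report as the source.

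**3. What central data remain.** Scheduled post-baseline laboratory visits (SAP Tables 2 and 5):

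- Double-blind part: Week 4, so 1 visit.
- Single-blind part: Weeks 6, 12, 20, 28 and 36, so 5 visits.
- Withdrawal part: Weeks 40, 44 and 48, so 3 visits.

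One local-only visit removes 1 of 1, 1 of 5 or 1 of 3 scheduled central values respectively. The first case needs Week 4 to be remote with no make-up central sample in that part. The addendum calls Week 4 a key visit, widens its window to ±1 week, and asks sites to contact the sponsor if that fails.

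**4. When the loss is certain.** Under the make-up rule, an abnormality is surely lost only if it has resolved by the next central sample, if the make-up visit is skipped and the abnormality does not last until the next visit, or if no later central sample exists. If it persists, the next on-site sample can count it.

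**5. Illustrative worst case.** Suppose Visits 8, 9 and 10 (Days 84, 140 and 196) are all local-only.

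- Share of the scheduled samples over the double-blind and single-blind parts: 3 / (1 + 5) = 3/6 = 50%.
- Longest gap, with Visit 7 at its earliest (42 − 2 = Day 40) and Visit 11 at its latest (252 + 56 = Day 308): 308 − 40 = 268 days, or 268/7 = 38.3 weeks.
- What this requires: the visits are 140 − 84 = 56 days apart, so each on-site visit must be impossible for about 56 − 7 = 49 days, three times running.

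**The case against.** The case for leaving the SAP alone has real substance.

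- **Central-only summaries are defensible.** They keep one set of reference ranges, and local values stay visible in listings. This stands for change-from-baseline summaries. It is weaker for a count of subjects crossing a threshold, where leaving out a known value can only lower the count.
- **The make-up visit limits the loss.** A reader might infer that these subjects' abnormalities never reach the tables. The addendum does not support that, because the on-site visit is normally still due and laboratory tests are scheduled at every visit from Week 4 except Week 38.
- **The courier case is different.** A reader might add the rule in addendum 2.1.1 that "a portion of the sample is used to measure the following safety parameters by the site's local laboratory". There the local test is additional and samples are frozen for delayed assessment, so central values can still follow. It does not support the point.
- **Adverse events of special interest are unaffected.** A reader might think that anaemia and hepatic signals are hidden. SAP 14.3 defines those events by coded adverse-event terms, and adverse events are asked about on the call.
- **The worst case is not typical.** The 50% and 268-day figures stack several unlikely conditions and fall mainly in the single-blind part, where everyone receives aprocitentan 25 mg. Investigators may also skip single-blind visits, and a gap arising that way is not due to SAP 7.3.1. Nothing in the documents suggests that the loss differs between arms.
- **Selectivity can be argued either way.** Subjects outside the defined group have no mandated bloods at a remote contact, so counting local values gives the defined group extra chances of detection. This stands, and is why the local-only count should be shown separately.

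**Conclusion.** The point holds in a limited form. As the SAP is written, an abnormality seen only on a local result from a COVID-19 remote contact is listed but not counted in the marked-abnormality or AST/ALT with bilirubin tables, and no pandemic provision changes this. The effect on the counts runs in one direction, towards too few.

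Its size cannot be computed, because the documents do not give the number of subjects with local-only results. It is confined to remote contacts at affected sites during the affected period, and is certain only in the circumstances of step 4. The 3-of-6 and 268-day figures illustrate what the rules permit and are not an estimate.

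The conclusion assumes that the local-results sentence overrides the one on unscheduled assessments, and that home-drawn samples were analysed locally. The main protocol was not available, so any retest rule in its Section 7.2.3.5 could not be checked. This is an inexpensive improvement to safety reporting and has no bearing on the efficacy analyses.

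**What to change.** In SAP 7.3.1 and 7.3.2:

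1. State that where a visit window has no central result, local haemoglobin, creatinine, eGFR, ALT, AST and total bilirubin from COVID-19 remote contacts count in the marked-abnormality and AST/ALT with bilirubin tables, or in a supplementary version of them.
2. For ULN-based thresholds, use the local laboratory's reference range where it was collected. The low-haemoglobin and eGFR thresholds are absolute and need none.
3. Footnote the number of subjects who qualify on local results only, by study part and treatment group.
4. Keep change-from-baseline summaries central-only.
5. Add 7.3 to the list in SAP 2.4.

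The cost is a few sentences and some programming. Local-laboratory eCRFs exist, but the documents do not say that the remote-contact results, or their ULNs, were entered there; this should be confirmed first. The main downside is that results from different laboratories are mixed in a count table, which the footnote makes visible. Where a threshold is relative to baseline, a local value may be set against a central baseline. The window condition also leaves a gap: a transient local abnormality followed by a normal central result in the same window stays uncounted, and the listing remains the place to see it.
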